For each outcome event and for each study cohort, the number of first events, total person-years for the event, number of first events per person-years (rate), the rate ratio (RR) and the VE, calculated as (1 - RR)) will be presented. This will also be provided per age group and per frailty score. Finally, VE will also be provided in shorter periods after dose 1, and between the doses, and by presence of comorbidities. Poisson regression will be used to estimate rates using the matched dataset, adjusting for the matching variables and body mass index (BMI), smoking, prescribed medications, and frailty score.

RAVEN extension analyses (other than VE):

- a) Populations at risk: Exploratory analysis of populations at risk of breakthrough COVID-19 and populations with a contraindication to vaccination will be carried out with the aim to better describe these populations at risk of COVID in a highly vaccinated population (e.g. to identify populations, and estimate their size). Artificial intelligence/machine learning (AI/ML) methods will be employed to predict breakthrough cases, time to vaccine waning and predictors of accepting booster doses.
- b) HCRU and health care cost related to COVID-19: The non-linear trends over time in healthcare service use and costs will be explored using inverse probability weighted generalized estimating equations (GEE). Estimates of the incremental health service use and incremental health service costs associated with receipt of COVID-19 vaccine will be over 1, 3 and 6 months of follow-up.
- c) Household incidence/transmission: Vaccinated and non-vaccinated cases with a positive SARS-CoV-2 test will be identified (index cases), along with their household contacts. The proportion of unvaccinated and vaccinated contacts who test positive for SARS-CoV-2 after the index case (secondary cases) will be compared among the vaccinated and non-vaccinated index cases. Logistic regression will be used to estimate the odds (and 95% confidence intervals (CI)) of being a secondary case, adjusting for confounders.
- d) Long COVID: Cases of long COVID will be described, including by initial COVID-19 disease severity. The impact of vaccination on the occurrence of long COVID (in vaccinated individuals, in vaccinated individuals with COVID-19) will be explored.

Milestones

Expected data collection:	
Interim reports:	
Final report:	

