9.3.3 Other Variables and Covariates

Table 6. Variable categories and data sources

Variables	Categories	Data source	Comment
Age	Different categorizations may be used -12 <50; 50-<65; 65-<70; 70-<80; 80+ -18-<40; 40-<50; 50+; 65+; 70+; 80+	GDPPR	BMI is binary as obese or not using HES, SUS, GDPPR or BMI can be created from weight/height if
Gender	Male/Female	-	available;
Ethnicity	White, Black, Asian, Other, Mixed		
Region	NHS Region	-	
Sociodemographic	Socioeconomic status – Index of Multiple Deprivation (IMD)		
BMI	-Obese (BMI 30+) -Not-obese (BMI <30)		
Smoking	- Current - Past - Non smoker		
Comorbidity	Specific comorbidities known to relate with increased risk of severe COVID- 19 and/or suboptimal vaccine response and/or vaccine contraindication including chronic respiratory disease, chronic kidney disease, chronic heart disease and vascular disease, chronic liver disease, chronic neurological disease, diabetes mellitus, severe mental illness, morbid obesity, asplenia or dysfunction of the spleen, and immunosuppression due to disease or treatment.	ORCIHD, HES and GDPPR	Follow JCVI/Green book list of comorbidities (COVID-19 Greenbook chapter 14a) Using ICD or SNOMED codes to identify comorbidities during the baseline period. For immunosuppressant medications, see Prescribed medication section below.
CMMS	0, and by quartile		Created from specific comorbidities;
Non-COVID-19 vaccination	 Flu vaccination (Y/N) Receive adequate vaccination (Y/N) 	GDPPR	An algorithm will be developed to determine if an individual is adequately vaccinated according to recommended vaccination schedule by age and comorbidity status
Prescription medication	Immunosuppressant vs. not	GDPPR	Prescribed medications at baseline will be grouped into immunosuppressant or not.
LTC /assisted living care facility	Yes/No	Not in any database	To be created for people aged 70+ by comparing their zip codes and LTC

Variables	Categories	Data	Comment
		source	
			address; or vaccination at LTC facility. (ORCHID)
Household composition	Size and age combination.	ORCHID UKHSA VE cohort	Available for 7.2 million subset of ORCHID
Frailty score	eFI grouped into - Mild - Moderate - Severe	Derived from GDPPR	Use an algorithm already developed to derive eFI, only available for population 65years and older. For this sub-group analysis.

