9.7 Data Analysis

9.7.1 Statistical Methods – General Aspects

A detailed SAP will be developed for this analysis. The SAP may modify the plans outlined in the protocol; any major modifications of primary endpoint definitions or their analyses would be reflected in a protocol amendment. For all study designs, p-values will be quoted to two decimal places, unless they are less than 0.001 (whereby the p-value will be given as < 0.001) or between < 0.005 and > 0.001, in which case they will be stated to three decimal places. Parameter estimates will be reported with 95% CIs. All statistical tests are 2 sided and with a 5% significance level.

A CONSORT 2010 Flow Diagram of the study population detailing each step of the inclusion and exclusion criteria applied will be generated. As indicated in section 9.4, to obtain the most followup data, the primary analysis will include all HES data until 8 weeks prior and all raw hospitalization data (SUS) from 8 weeks to 2 weeks prior database lock. A sensitivity analysis including only HES data, therefore a shorter follow-up for hospitalization, will also be done.

For the concurrent control arm, each week starting from 8th December 2020, we will match all newly vaccinated persons in a 1:1 ratio to unvaccinated controls (Dagan et al, 2021). Newly vaccinated persons will be eligible for inclusion in the study, even if they will have previously been selected as a control. We will match vaccine recipients and controls on variables associated with the probability of both vaccination and infection or severity of COVID-19: age (study defined age bands), gender, general practice, (or NHS Region), and comorbidity as defined by CMMS quartile. We will exact match each week (if feasible). To assess the quality of matching, love plots will be created showing the mean standardized difference between each vaccinated cohort (AstraZeneca or other vaccine cohort) and the comparator cohorts in participants' characteristics. If important differences are observed, the matching criteria will be refined.

The demographic and characteristics of study participants in each vaccine arm and its respective control arm at baseline will be determined during the 12-month period before index date using the measurement closest to index date.

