Summary tables of all patient characteristics and end points indicated in section 9.3.2 will be created for both the before and after matching situation to provide insight in population characteristics as well as in errors and missingness. Categorical variables will be checked on meaningful categories and frequencies. It is not anticipated that categories will have too low frequency. Pooling will be considered when the frequency for a category becomes below 1000.

Continuous variables will be summarized in terms of min, max, interquartile range, median and mean to get insight in these variables, but also to provide a first indication of use of same unit across the database and to obtain a first impression about possible transformations needed. Missing values will be considered in detail. If the percentage of missingness is below 10%, complete case analyses will be performed. When exceeding 10%, multiple imputation will be run additionally based on the total dataset.

For each outcome event, the summary tables will present for each study cohort the number of first events, total person-years for the event and number of first events per person-years (rate), the RR and the VE which is calculated as 1 - RR. This will also be provided per age group and per frailty score where further stratification/subgroups are indicated below. Finally, VE will also be provided in shorter periods after dose 1, and between the doses, and presence of comorbidities.

Poisson regression with offset for time at risk will be used to estimate rates using the matched dataset, adjusting for the matching variables and BMI, smoking, prescribed medications, and frailty score, which are known to increase risk of hospitalization and death and are likely associated with vaccination.

Checks on linearity for continuous variables will be performed. In order to evaluate interactions of independent variables with the exposure (i.e. vaccinated/comparator), continuous variables will be categorized and the VE will be tabulated per category. For variables for which the maximum and minimum VE across categories is more than 10% different, interaction effects with the exposure will be taken into account in the Poisson model. For interactions among independent variables that are not the exposure, interaction variables will be created. Forward selection is performed, and interaction variables will be included when the computed VE changes with more than 10%.

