Characteristics of each comparator group will be compared using t-tests for continuous variables and chi-square tests for categorical variables. Initial exploration of the data will be conducted to guide selection of the appropriate analytic strategy. Inverse probability weighted GEE (Salazar et al., 2016) will be used to model non-linear trends in healthcare service use and costs over time, accounting for missing data, and adjusting for the matching variables and BMI status, smoking status, and frailty score. In the models, the total follow-up period will be divided into time intervals and interval-specific weights calculated as the inverse cumulative product of the probability of being observed up to a given interval using the method of van der Wal and Geskus (2011). Inverse probability weighting ensures that observations with a high probability of being missing (for example costs incurred in the later months of follow-up) are given more weight than observations with a low probability of being missing (for example costs incurred in the earlier months of follow-up) (Glick et al., 2015).

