Adjusted estimates of cumulative healthcare utilisation counts, lengths of stay and costs, and between-group difference in counts, length of stay and costs, will be obtained from the regressions by summing interval-specific estimates over the time period of interest, a strategy originally reported by Lin (2000). Standard errors and confidence intervals around the mean estimates will be obtained via the robust variance/sandwich estimator, which provides a degree of robustness to departures from normality of errors and misspecification of the GEE working correlation matrix. An alternative approach for estimating standard errors and 95% confidence intervals is through the use of non-parametric bootstrapping. This would involve randomly sampling individual patients with replacement from the data to generate, for example, 1000 replicate datasets, and then fitting regression models to each replicate dataset and calculating adjusted bootstrap estimates of cumulative counts, lengths of stay and costs and the respective between-group differences. However, we recognise that the non-parametric bootstrap method can be computationally expensive for large sample applications such as ours. As a sensitivity check of the results generated by our primary modelling approach, we will therefore also apply the nonparametric bootstrap method to a smaller sample of data to obtain bias-corrected standard errors and confidence intervals. For completeness, the analyses will be repeated by restricting to patients with complete data over 1, 3 and 6 months of follow-up. The approaches to handling potential confounding will mirror those adopted by the statistical analyses. The analyses will also be repeated by the subgroups pre-specified by the statistical analyses.

We will also report the health care resource use and health care costs by COVID-19 risk group, using the JCVI risk group classification.

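### The covariate list for the use and cost model in 9.7.6.2 omits prescribed medications, although the effectiveness model includes them and the same section says confounding is handled alike

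*Protocol*

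**What the plan says.** The effectiveness analysis (Protocol 9.7.1) is a Poisson regression on the matched data, "adjusting for the matching variables and BMI, smoking, prescribed medications, and frailty score". The synopsis gives the same set: "adjusting for the matching variables and body mass index (BMI), smoking, prescribed medications, and frailty score". Section 9.7.1 justifies these covariates as ones "which are known to increase risk of hospitalization and death and are likely associated with vaccination". Table 6 (9.3.3) says what the medication term means: "Prescribed medications at baseline will be grouped into immunosuppressant or not".

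The economic analysis (Protocol 9.7.6.2) models use and cost by inverse probability weighted GEE, "adjusting for the matching variables and BMI status, smoking status, and frailty score". Later in the same section: "The approaches to handling potential confounding will mirror those adopted by the statistical analyses".

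**The concern.** Section 9.7.6.2 contains two instructions. One is an explicit covariate list without medications. The other is a general rule to treat confounding as the effectiveness analysis does, which brings medications in. An analyst who works from the explicit list fits a different adjustment set from the effectiveness model, and the protocol gives no reason for the difference.

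The missing term is a confounder by the protocol's own account in 9.7.1, which links it to hospitalization and to vaccination. Hospital admissions are one of the cost categories in 9.7.6.2, so the reasoning carries over to cost. The economic objective also covers groups with a suboptimal vaccine response, and people who are immunocompromised are the main population of interest for that part of the extension. At stake are whether the incremental use and cost figures are adjusted for treatment-related immunosuppression, and whether the cost and effectiveness results rest on the same adjustment.

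**Working it through.** **1. The two adjustment sets side by side.**

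| Term | Effectiveness model (9.7.1, synopsis) | Use and cost GEE (9.7.6.2) |
|---|---|---|
| Matching variables | yes | yes |
| BMI | yes | yes |
| Smoking | yes | yes |
| Frailty score | yes | yes |
| Prescribed medications | yes | no |

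The effectiveness set exceeds the cost set by exactly one term, and the cost set contains nothing that the effectiveness set lacks.

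**2. Can another term stand in for it?**
- Comorbidity is matched in 9.7.1, but only as "comorbidity as defined by CMMS quartile". A quartile of a summary score can contain both users and non-users of immunosuppressants, so matching on it does not equalise use between arms. It may remove part of the imbalance.
- The frailty score is "only available for population 65years and older" (Table 6). Below 65 it carries no information.

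**3. Is the omission justified because prescriptions are themselves a cost?** Primary care prescriptions are a cost category in 9.7.6.2. The covariate, however, is measured at baseline, before follow-up costs accrue. Adjusting for it does not adjust for the outcome.

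**4. Scale.** The plan states no figure to reproduce, and it gives neither the prevalence of immunosuppressant use by arm nor its cost. The values below are assumptions that show only the order of magnitude.

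On the difference scale, which is the stated aim of 9.7.6.2:

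bias in incremental cost = (residual difference in prevalence) × (added cost per user), both given the other covariates.

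- 0.5 percentage points and GBP 1,000 over six months: 0.005 × 1,000 = GBP 5 per person.
- 2 percentage points and GBP 5,000: 0.02 × 5,000 = GBP 100 per person.

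On the ratio scale, with prevalences p_v (vaccinated) and p_c (control) and a cost ratio r of users to non-users:

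bias = [1 + p_v(r − 1)] / [1 + p_c(r − 1)] − 1.

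| p_v | p_c | r | Calculation | Bias |
|---|---|---|---|---|
| 4% | 3% | 2 | 1.04/1.03 − 1 | +1.0% |
| 4% | 3% | 4 | 1.12/1.09 − 1 | +2.8% |
| 5% | 3% | 4 | 1.15/1.09 − 1 | +5.5% |
| 3% | 4% | 4 | 1.09/1.12 − 1 | −2.7% |

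The last row swaps the arms of the second. The sign follows whichever arm has more users after matching.

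**5. Against sampling error.** The standard error of the log cost ratio is about CV × √(2/n), for n per arm and a coefficient of variation CV of cost, which is also assumed. With n = 200,000, CV 5 gives 1.6% and CV 10 gives 3.2%. A bias of 2.8% lies above the first and below the second. Whether the bias would stand out from sampling error therefore depends on a cost variability that the protocol does not give.

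**The case against.** The strongest reply is that the protocol already contains the remedy. The list in 9.7.6.2 is not said to be exhaustive, and an analyst who follows the mirror sentence would include medications and satisfy both statements. The section also lets initial data exploration guide the analytic strategy, and 9.7.1 leaves detail to the SAP. This stands in part: the gap arises only if the explicit list governs. But a named covariate list is what usually gets programmed, and nothing in the text tells the analyst that the general sentence overrides it.

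There are also partial safeguards. Balance in participants' characteristics is checked with love plots, and the matching may be refined (9.7.1). The cost analyses are repeated in the subgroups of the statistical analyses, which may include immunosuppressant medication (9.7.2), and costs are reported by JCVI risk group. These could expose an imbalance, but they do not put the term into the overall estimate.

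A reader might infer that the omission loads cost onto the vaccinated arm and so understates any saving. The documents do not settle this. Section 9.1 reports early vaccination of people aged 16 to 64 with comorbidities, which points that way. The same section says the control arm may include people in terminal care, and the synopsis recognises people with a contraindication to vaccination. The residual difference after matching could run either way.

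**Conclusion.** The mismatch is real. The list in 9.7.6.2 lacks one covariate that 9.7.1 and the synopsis include, with no reason given, and it sits badly with the mirror sentence in its own section. If that list is fitted as written, the incremental use and cost estimates are open to residual confounding by immunosuppressant use.

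Three stronger readings are not supported. It does not follow that the cost estimates will be confounded, because the mirror sentence, if followed, brings the term in, and CMMS matching may absorb part of the effect. Neither direction nor size can be derived from the documents: GBP 5 to 100 per person, or about 1% to 5.5% of cost, rests wholly on assumed prevalences and costs. Nor can it be said that the bias must exceed the standard error.

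The point concerns one extension objective. The primary effectiveness estimate is not affected, and this is a minor but almost free correction.

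**What to change.** In 9.7.6.2, add baseline prescribed medications (immunosuppressant yes/no, as in Table 6) to the GEE covariate list, so that it matches 9.7.1 and the synopsis and agrees with the mirror sentence. If the omission is deliberate, state the reason and amend that sentence instead.

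The mismatch does not require a change to the model for the observation weights. The protocol lists no covariates for that model, and the effectiveness analysis describes no such weights to mirror.

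The cost is one covariate that is already defined and planned for extraction. No other figure or analysis in the protocol changes.

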The adenovirus vector ChAdOx1 vaccine technology has been used in the past for the development of candidate vaccines against several infections, including influenza, Zika, and MERS (Antrobus et al, 2014, Folegatti et al, 2020, López-Camacho et al, 2018). Oxford University has adapted and transferred the platform technology used against MERS-CoV to develop a vaccine against SARS-CoV-2, resulting in the rapid development of a vaccine against this infection. The Oxford/AstraZeneca COVID-19 vaccine (AZD1222) is a recombinant replication-defective chimpanzee adenovirus expressing the SARS-CoV-2 S surface glycoprotein (Folegatti et al, 2020). AZD1222 has been shown to be highly efficacious in pivotal randomized clinical trials (RCT), demonstrating 82% overall efficacy against symptomatic infection and 100% efficacy against severe infection. Recent unpublished data from the phase 3 pivotal trial in the United States showed high efficacy (85%) in people 65 years of age or older, and again confirmed 100% efficacy in preventing severe cases. Although a high level of single dose efficacy has been demonstrated in clinical trials between 3 and 12 weeks and confirmed in early effectiveness studies conducted in the United Kingdom (UK), clinical trials and effectiveness study so far have not included detailed vaccine-specific analysis by age group, co-morbidities, nor have they assessed vaccine impact on critical care admission, mortality, and overall outcomes. Similarly, there are few studies taking into account the COVID-19 variant, these data have been aggregated on a national basis by the UK COVID-19 Genomics consortium (UK COG) since September 2020 (Mishra et al, 2021). Thus, it remains important to better understand VE by ages, time intervals between doses, and to determine if single dose effectiveness may extend beyond 12 weeks.

Given mortality due to COVID-19 is highest in long-term care and assisted living facilities and since the Oxford/AstraZeneca vaccine is prioritized for these facilities due to its ease of reach, it is useful to understand the impact of Oxford/AstraZeneca vaccination on hospitalization and mortality for elderly people in these facilities. It's also important to assess VE by age groups and comorbidities for best guidance for COVID-19 immunization programs.

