9.2.4 Participant Follow-up

For the vaccinated and concurrent control arms, study participants will be followed from the index date to the end of the study, loss to follow-up (deregistration), vaccination (for unvaccinated controls), vaccination of the matched control (for vaccinated people), or death, whichever is earlier.

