9.7.6.2 Health Care Resource Use and Health Care Cost Related to COVID-19

The objective of the economic analysis will be to estimate incremental health service use and incremental health service costs associated with receipt of at least one dose of the Oxford/AstraZeneca COVID-19 vaccine (the AstraZeneca vaccine arm) or at least one dose of other COVID-19 vaccines (the other COVID-19 vaccine arm) over the short (one and three months of follow-up) and medium term (six months of follow-up) and to disaggregate incremental costs by cost category. Our comparator groups and their construction will mirror those proposed for the statistical analyses, namely: (i) the AstraZeneca vaccine arm; (ii) the other COVID-19 vaccine arm; (iii) the concurrent control arm. The approaches to matching participants based on age group, gender, region, comorbidity status and practice, and to defining the date of study entry, will mirror those proposed for the statistical analyses.

Cumulative health care service use and health care costs covering primary and secondary health care services over 1 month, 3 months and 6 months of follow-up will be estimated using data extracted from the data assets listed in Section 9.4, and grouped by the following clinical settings and resource categories:

- Primary care consultations;
- Primary care prescriptions;
- Primary care medical tests and investigations;
- Hospital outpatient attendances and procedures;
- Hospital A&E (emergency department) attendances without admission
- Hospital admissions, inpatient, and day cases.

Primary and secondary care services will be valued by attaching unit costs derived from national compendia to resource inputs. All costs will be expressed in pounds sterling and valued at 2021 prices with unit costs estimated at earlier price dates inflated to 2021 prices using the NHS Hospital and Community Pay and Prices Index.

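### The cost analysis (9.7.6.2) does not separate death from censoring; read literally, post-death intervals count as missing rather than zero, biasing incremental cost when mortality differs by arm

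*Protocol*

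**What the plan says.** - **Follow-up.** Protocol 9.2.4 gives the only rule for the end of follow-up: end of study, deregistration, vaccination of a control, or "vaccination of the matched control (for vaccinated people), or death, whichever is earlier". Death has no separate role.
- **Target quantity.** Section 9.7.6.2 estimates cumulative use and "health care costs covering primary and secondary health care services over 1 month, 3 months and 6 months of follow-up", and the differences between arms.
- **Weights.** The model is an inverse-probability-weighted GEE with "interval-specific weights calculated as the inverse cumulative product of the probability of being observed up to a given interval". The stated purpose is to account for missing data, so that "observations with a high probability of being missing (for example costs incurred in the later months of follow-up) are given more weight" than those unlikely to be missing. Death is not mentioned.
- **Summation.** Cumulative cost is the sum of the interval-specific regression estimates. There is no survival term and no rule for intervals after death.
- **Rerun.** For completeness, "the analyses will be repeated by restricting to patients with complete data over 1, 3 and 6 months of follow-up". Whether someone who died within the horizon has complete data is not stated.

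**The concern.** Once a person has died, later use and cost are known to be zero. They are not missing. If death is handled like deregistration, the weights make survivors stand in for the dead, and the model estimates cost as though nobody left the cohort by dying. The rerun goes further: a person who dies in month 2 lacks six months of data and is excluded, along with the cost of the terminal admission.

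This would matter little if deaths were balanced, but the study expects imbalance. COVID-19 death is a primary outcome and all-cause mortality a secondary one (9.3.2), and section 7 describes the vaccine as "demonstrating 82% overall efficacy against symptomatic infection and 100% efficacy against severe infection". The error would then differ by arm and enter the incremental cost, which is the quantity wanted for extension objective 2.

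**Working it through.** The protocol states no cost, mortality or precision figure for this analysis, so there is nothing of its own to reproduce. The check asks how large the error is if the text is applied literally. **All cost and mortality inputs below are assumptions.**

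**Model.** Six one-month intervals; *q* is six-month mortality; cost is £300 per month alive (both arms) and £4,000 in the month of death.

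- Monthly death hazard: h = 1 − (1 − q)^(1/6)
- Mean cost of an interval among those alive at its start: m = 300(1 − h) + 4000h
- True mean cost, zero after death: m × Σ(1 − h)^k, k = 0 to 5
- Death treated as missing (weighted): 6m
- Complete data only, the dead dropped: 6 × 300 = 1,800

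**Worked case, 3% vaccinated vs 6% control.**

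| | h | m | Σ(1 − h)^k | True | Death as missing | Complete only |
|---|---|---|---|---|---|---|
| Vaccinated | 0.00506 | £318.74 | 5.925 | £1,888.4 | £1,912.4 | £1,800 |
| Control | 0.01026 | £337.96 | 5.848 | £1,976.5 | £2,027.8 | £1,800 |
| Difference | | | | −£88.1 | −£115.3 | £0 |

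**Across mortality levels (vaccinated minus control).**

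| Mortality | True | Death as missing | Shift | Relative | Complete only |
|---|---|---|---|---|---|
| 0.5% vs 1% | −£14.7 | −£18.6 | −£3.9 | 26% | £0 |
| 3% vs 6% | −£88.1 | −£115.3 | −£27.3 | 31% | £0 |
| 5% vs 10% | −£146.3 | −£197.5 | −£51.1 | 35% | £0 |

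**Alive-cost also differing by arm.** With control alive-cost at £310, £330 or £350 and vaccinated at £300, the 3% vs 6% case gives a shift of £29, £32 or £35, a relative error of 20%, 12% or 9%, and complete-data differences of −£60, −£180 and −£300. At 0.5% vs 1% the relative error is 5.5%, 2.4% or 1.6%. The absolute shift stays. The £0 in the tables follows from setting alive-costs equal.

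**Lower terminal cost.** At £1,000 in the month of death and 3% vs 6% mortality, the true difference is +£1.9 and the weighted one −£21.8, so the sign changes.

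**Second model.** Here the assumptions are £200 per month alive, control mortality 5% and a death rate ratio of 0.2; the month of death costs half a month's alive-cost plus the terminal cost.

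- Terminal cost £5,000: true −£175.8, death as missing −£201.1, complete only £0. The weighted estimate is too low and the rerun too high.
- No terminal cost: true +£24.2, death as missing +£4.1, complete only £0. Both are too low.
- Death rate ratio 1.0 and equal costs: the bias cancels.

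**Does the remedy work?** A simulation of the £5,000 case (2 million per arm, 10% independent censoring per month) gave a true difference of −£174.9. Keeping the dead as observed zeros and weighting for censoring only gave −£174.9; death as missing gave −£200.1; complete data gave £0.

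**The case against.** The strongest reply is that the protocol is silent here, not wrong. No sentence says that intervals after death are missing. If cost after death is known to be zero, missing data need not include the dead, and a person followed to death may count as complete. The follow-up rule in 9.2.4 suits the event-rate analyses. Section 9.7.6.2 says that matching and the approach "to defining the date of study entry, will mirror those proposed for the statistical analyses", and it also mirrors comparator groups, confounding control and subgroups, but the end of follow-up is not on that list. A detailed SAP is promised, and 9.7.6.2 says data exploration will guide the choice of strategy. The cited method papers may settle the matter, but they cannot be checked here and neither side can lean on them.

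Much of this stands. A reader might infer that the protocol prescribes up-weighting survivors to replace the dead; it does not say so. A reader might also take 31% as the size of the error. That figure depends on death being the only cost difference between arms, although hospitalisation and ICU admission are also primary outcomes and could plausibly make alive-costs differ.

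What does not stand is that this is merely SAP detail. The protocol itself fixes the weight formula, the summation and the restricted rerun, and 9.2.4 is the only rule saying when observation ends. A programmer applying those sections as written would have no zero-cost intervals after death and would exclude the dead from the rerun.

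**Conclusion.** The point holds in conditional form. The cost estimator, applied as worded with the only follow-up rule available, treats time after death as missing and removes people who died from the complete-data rerun. The incremental cost is then biased if mortality differs by arm. Whether it would be implemented that way is left open.

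On assumed costs of £300 per month alive and £4,000 in the month of death, the weighted estimate moves by about £4 per person at 0.5% vs 1% mortality and about £27 at 3% vs 6%. It would matter most in older or frail strata, and 9.7.6.2 repeats the analysis by subgroup and by risk group. A reader might infer that the weighted analysis and the rerun err in opposite directions and so bracket the truth. That happens when terminal costs are high, but with no terminal cost both err the same way, so the rerun is not a safe check on the main model.

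The consequence is confined to extension objective 2. Primary and secondary vaccine effectiveness results are untouched. The clarification should be made before the cost analysis is programmed.

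**What to change.** Add to 9.7.6.2, and carry into the SAP:

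1. People who die remain observed, with use and cost set to zero in every interval after death; costs up to and including the interval of death are kept.
2. The observation weights model only deregistration, vaccination (the person's own, or that of the matched control) and end of available data. Death is not a censoring event in the cost analysis, notwithstanding 9.2.4.
3. Complete data over 1, 3 or 6 months means observed to that horizon or to death, whichever comes first.

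The cost is a few lines of text and minor programming. No new data are needed, because dates of death are already among the linked sources (9.3.2 and 9.4).
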